6. DRUG DISPENSING, ACCOUNTABILITY AND DESTRUCTION

 KNO_3 and KCI capsules will be prepared at the University of Pennsylvania Investigational Drug Service [[name]]. Drug bottling, labeling and dispensing will also be managed by the Penn Investigational Drug Pharmacy. Prior to initiation of each phase, participants will receive a sufficient supply of KNO3 or control capsules to last until the end of each treatment phase, allowing for 100% compliance with the regimen for the entire treatment phase, including a window of ± 7 days for the 1-week uptitration (to ensure an adequate supply of medication before additional medications are received by the subject) and ± 1 week for the endpoint assessment visit.

Subjects will be instructed to take the medication as required by the protocol, and compliance will be assessed via pill count performed by IDS.

Subjects will be instructed to return unused capsules at the end of each treatment phase. A pill count will be performed by IDS prior to destruction of the drug. Returned trial capsules will be stored separately from the non-allocated trial capsules until returned trial capsules are disposed of. The IDS personnel will keep track of all received, used, partly used and unused trial products.

Used and unused study drug will be destroyed at the instruction of the sponsor. A copy of the drug destruction SOP should be maintained in the pharmacy section of the Regulatory Binder. Study drug should not be destroyed until drug accountability has been completed.

6.1. Rules for un-blinding

Randomization data will be kept strictly confidential, accessible only to authorized IDS personnel, until the time of un-blinding. The investigators will be given access to the treatment code for their patients for emergency un-blinding by calling the IDS. This is considered to be a very unlikely occurrence. Any suspected study drug-related events will be treated as though the patient received active (KNO₃). Nevertheless, in the rare event of necessary un-blinding, the site PI and the sponsor must be notified.

7. ADVERSE EVENTS

7.1. Key definitions

Adverse Event: An adverse event (AE) is any untoward medical occurrence associated with the use of a drug in a subject whether or not considered drug or biologic related. An AE can therefore be any unfavorable and unintended sign, symptom or disease temporally associated with the use of the pharmaceutical product.

Suspected Adverse Reaction: A suspected adverse reaction (SAR) is any adverse event for which there is a reasonable possibility that the drug caused the event. "Reasonable possibility" suggests there is a causal relationship between the drug and the adverse event. "Suspected adverse reaction" implies a lesser degree of certainty about causality than adverse reaction, which means any adverse event caused by a drug

Serious Adverse Events (SAE): An adverse event or suspected adverse reaction is considered serious if the investigator or sponsor believes any of the following outcomes may occur:

- Death
- Life-threatening AE: Places the subject at immediate risk of death at the time of the event as it occurred. It does not include an AE that, had it occurred in a more severe form, might have caused death.
- Persistent or significant incapacity or substantial disruption of the ability to conduct normal life functions.

- Inpatient hospitalization or prolongation of hospitalization.
- Congenital anomaly or birth defect.
- Important medical events that may not result in death, be life threatening, or require hospitalization may be considered a serious adverse event when, based upon appropriate medical judgment, they may jeopardize the subject and may require medical or surgical intervention to prevent one of the outcomes listed in this definition above.

This determination is based on the opinion of either the investigator or sponsor (e.g., if either believes it is serious, it must be considered serious).

Unanticipated Adverse Device Effect (ADE): Any serious adverse effect on health or safety, any life-threatening problem or death caused by, or associated with a device, if that effect, problem, or death was not previously identified in nature, severity, or degree of incidence in the application; or any other unanticipated serious problem associated with a device that relates to the rights, safety, or welfare of subjects.

7.2. Classification of AE/ADEs regarding causal relationship to study interventions and severity

A medically-qualified investigator must assess all AEs in terms of causal relationship to intervention, severity, and "expectedness" using the following guidelines:

Classification of Adverse Events for Causal Relationship to Study Interventions					
Not related	There is not a reasonable causal relationship to the investigational product and the adverse event				
Unlikely related	No temporal association or the cause of the event has been identified, or the drug or device cannot be implicated.				
Possibly related:	There is reasonable evidence to suggest a causal relationship between the drug and adverse event.				
Related	There is evidence to suggest a causal relationship, and the influence of other factors is unlikely.				

Classification of Adverse Events Regarding Severity Scale

1	Mild AE. Awareness of sign, symptom, or event, but easily tolerated; no treatment required
2	Moderate AE. Discomfort enough to cause interference with usual activity and may warrant intervention. In the latter scenario, AE responds to treatment
3	Severe AE. Incapacitating, limiting usual/normal activities or significantly affects clinical status requiring hospitalization or prolongation of hospitalization.
4	Life-threatening or disabling
5	Fatal AE

Expectedness: The expectedness of an AE/ADE or SAR shall be determined according to the specified reference document containing safety information (e.g., most current investigator's brochure or product label). Any AE/ADE that is not identified in nature, severity, or specificity in the current study reference document(s) (e.g. protocol or investigator's brochure) is considered unexpected. Events that are mentioned in the investigator's brochure as occurring with a class of drugs or as anticipated from the pharmacological properties of the drug, but not specifically mentioned as occurring with the particular drug under investigation are considered unexpected.

The following AEs are expected, disease-related events in patients post-transcatheter or surgical AVR (84).

- Unplanned hospitalization, ER visit or clinic visit
- Arrhythmias
- Permanent pacemaker implantation
- Sudden cardiac death
- Acute coronary syndrome
- Cerebrovascular event
- Paravalvular aortic regurgitation
- Wound dehiscence
- Infective endocarditis
- Aortic dissection
- Sternal infection
- Thromboembolism

The following are potential expected side effects of KNO3:

- Stomach discomfort
- Slight headache
- Dizziness
- Lightheadedness
- Low blood pressure
- Stomach Ache, diarrhea, nausea, or vomiting
- Shortness of breath
- Flushing
- Rash
- Mild orthostatic hypotension
- Clinically significant methemoglobinemia or significant symptomatic orthostatic hypotension (20 mmHg or greater reduction in systolic blood pressure with associated symptom such as dizziness) are potential side effects, although we will consider them unexpected given prior data in this patient population with this particular drug and dosing scheme.

7.3. Recording and Reporting of Adverse Events

The site PI will continuously supervise all aspects of the trial and review the records of the study

subjects following each visit and at the end of their participation. The site PI will be responsible for ensuring that all adverse events are noted, followed and reported to the IRB, Sponsor (at [contact]) and IND Medical Director as appropriate.

SAEs occurring from the time of signed informed consent to the final study visit will be captured on the SAE eCRF. AEs will be classified according to the guidelines/definitions specified in section 7 of the protocol. Any AE rated \geq 3 in severity (i.e., SAE) must be reported by the site investigator or qualified designee within 1 working day of first becoming aware of the event, to the sponsor via email and regulatory medical director. The IRB should be notified as per institutional guidelines. The medical director and site IRB, as appropriate, will make an immediate determination about the necessity to modify the protocol, include additional information in the consent form, inform previous participants, temporarily hold enrollment of patients, or terminate the study. The study will proceed only if the medical director and site IRB all agree on this course of action.

The investigator or qualified designee will enter the required information regarding the SAE into the appropriate module of the eCRF, All study procedures and cumulative adverse events are subject to full IRB review at least yearly.

Events significant enough to necessitate modification of study drug dosing will be captured on an appropriate eCRF module ("Study Drug Dosing" page). Should the PI determine that modification to the study drug is appropriate, the PI must notify the sponsor.

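### Section 7.3 ties the one-working-day report to severity grade 3 or higher and calls that set SAEs, which contradicts the outcome-based SAE definition in section 7.1

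*Combined protocol and SAP*

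**What the plan says.** Section 7.1 defines seriousness by outcome. An event "is considered serious if the investigator or sponsor believes any of the following outcomes may occur", and six criteria follow: death; threat to life; "Persistent or significant incapacity or substantial disruption of the ability to conduct normal life functions"; a new or prolonged hospital stay; "Congenital anomaly or birth defect"; and a judgement-based category, "Important medical events that may not result in death, be life threatening, or require hospitalization may be considered a serious adverse event". Either the investigator or the sponsor can make the call: "if either believes it is serious, it must be considered serious". Severity grade plays no part.

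Section 7.2 sets out a separate five-point severity scale. Grade 2 covers discomfort that interferes with activity and may need an intervention, to which the event then responds. Grade 3 reads "Severe AE. Incapacitating, limiting usual/normal activities or significantly affects clinical status requiring hospitalization or prolongation of hospitalization". Grade 4 is life-threatening or disabling, and grade 5 is fatal.

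Section 7.3 requires SAEs from consent to the last visit to be entered on the SAE eCRF. It then sets the timed rule, under which an adverse event graded 3 or higher "in severity (i.e., SAE) must be reported by the site investigator or qualified designee within 1 working day". The recipients are the sponsor and the regulatory medical director. The IRB is notified under institutional guidelines.

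**The concern.** Seriousness and severity are different classifications, and the protocol defines them separately. By joining them with an equating phrase, section 7.3 lets the grade decide which events get the one-day notice and also relabels the graded set as SAEs.

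Two things are at stake. The first is timing. Section 7.3 goes straight from this notice to the decision by the medical director and the IRB on whether to change, pause or end the study. The sponsor's power under 7.1 to call an event serious also depends on hearing about it promptly. The second is consistency. Section 1 names safety as a purpose of the trial, and with two working meanings of SAE in one section, different staff could classify the same event differently.

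**Working it through.** No figure is involved, so the check compares the 7.1 criteria with the 7.2 grades, applies the 7.3 trigger, and then looks for any other deadline.

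**Step 1. Serious events against the grade trigger**

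| Criterion in 7.1 | Nearest grade in 7.2 | Inside the grade 3 or higher trigger? |
|---|---|---|
| Death | 5 | Yes |
| Threat to life | 4 | Yes |
| Hospital stay, new or prolonged | Named in 3 | Yes |
| Incapacity or disrupted function | 3 or 4 | Largely |
| Congenital anomaly | None | Not necessarily |
| Important medical event | None; can fit 2 | Not necessarily |

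Four of the six criteria are wholly or largely caught. An important medical event is, by its own definition, one that need not be fatal, life-threatening or require admission. If it was treated and resolved on an outpatient basis, the grade 2 description can fit it. It is then serious under 7.1 and below the trigger in 7.3.

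**Step 2. Graded events against the SAE definition**

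Grade 3 has two limbs. The hospitalization limb matches 7.1. The limb on incapacity and limited activity matches only in part, because 7.1 asks for incapacity that is persistent or significant, or for disruption that is substantial. A short-lived severe event, such as a transient severe headache, could be grade 3 without meeting 7.1, and 7.3 would still label it an SAE.

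**Step 3. Is there another deadline for a serious event graded 1 or 2?**

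- Section 5.6 asks for timely reporting and defers to section 7 for the detail.
- The eCRF sentences in 7.3 carry no time limit.
- Section 7.5 is keyed to seriousness and not to grade, but only for events that are also related and unexpected. The sponsor's copy of that report follows the regulatory timeline, not the one-day rule.
- Section 7.5 points to 7.4 for procedures. Section 7.4 covers follow-up and gives no timeline.
- Section 7.6 puts pregnancy on the SAE timeline. The only timed SAE rule it can mean is the one in 7.3.
- Section 13 refers to Appendix 3, which is not in the text available for this review.

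In the available text, then, a serious event graded 1 or 2 and judged unrelated or expected has no deadline for notice to the sponsor and medical director. If it is related and unexpected, 7.5 applies, but the one-day notice does not.

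**The case against.** The strongest reply is that the equating phrase is loose wording with little practical effect. Several parts of that reply stand.

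- **Regulatory reporting.** A reader might infer that low-grade serious events escape expedited reporting to the authorities. The documents do not support this: 7.5 turns on seriousness, relatedness and unexpectedness, and grade does not enter.
- **SAE counts.** A reader might infer that reported SAE counts will be wrong. That is too strong. Section 7.3 requires SAE capture in its own sentence and says that events are classified by the section 7 definitions. Inconsistency is possible if staff follow the equating phrase, but it is not shown.
- **Grade 3.** It would be wrong to say that its activity limb has no equivalent in 7.1, since the incapacity criterion is a partial match. Over-inclusion also gives more early notice, not less.
- **Congenital anomaly.** This gap is close to moot. Participants are aged 50 to 90, pregnancy is an exclusion, and 7.6 puts any pregnancy on SAE timelines.
- **Other safeguards.** The site PI reviews records after each visit and must see that events reach the IRB, the sponsor and the IND medical director as appropriate. Such an event would therefore not simply go unreported.

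What does not stand is the claim that these safeguards close the gap. None of them sets a deadline for this notice. A site that followed 7.3 to the letter could comply and still omit a one-day report of an event that 7.1 calls serious. Appendix 3 may contain a better rule, but 7.3 would still conflict with 7.1.

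**Conclusion.** The contradiction between 7.1 and 7.3 is real and narrow. It affects the timing of notice to the sponsor and medical director for serious events graded 1 or 2, in practice mainly important medical events managed without admission. It also leaves open whether a transient grade 3 event counts as an SAE.

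Its size cannot be put as a rate. The documents give no expected number of SAEs by grade, and setting one event against the 22 subjects would say nothing about how often events are misrouted. Deaths, life-threatening events and hospitalizations remain inside the rule.

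The conclusion rests on reading 7.3 literally and on Appendix 3 holding no separate SAE deadline, which could not be checked. If Appendix 3 has one, the timing gap may close, but the conflict of definitions would remain. The point does not touch the efficacy analysis. It should be corrected because the change is small and the rule governs safety notice.

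**What to change.** Reconcile sections 7.1, 7.2 and 7.3 with two separate statements in 7.3:

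1. Any adverse event that meets the SAE definition in section 7.1, whatever its severity grade, is reported to the sponsor and the regulatory medical director within one working day of the site learning of it.
2. Any other adverse event graded 3 or higher is notified to the same recipients within the same time, and is not labelled an SAE unless it meets section 7.1.

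The second statement keeps every early notice that the present rule gives. Check Appendix 3 for agreement at the same time.

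The cost is about one sentence of protocol text and possibly a few more one-day reports. No dose, visit, endpoint or clinical rule changes.

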7.4. Follow-up

The Investigator will record safety follow-up information according to the same process used for reporting the initial event as described above. The Investigator will follow all reportable events until resolution, stabilization or the event is otherwise explained.

7.5. Management of Suspected Unexpected Serious Adverse Reaction

AEs that meet the criteria of serious, related to study intervention, and unexpected for the study intervention, qualify for expedited reporting by the sponsor to the regulatory authorities. The Site Investigator will assess all SAEs and evaluate for "unexpectedness" and relationship to study drug. The Site Investigator is required to complete a report for any events identified as serious, study drug related and unexpected, using the CIOMS format. The sponsor will submit a voluntary CIOMS form. See Section 7.4 for reporting procedures.

A copy of this report should be kept at the site and also forwarded to the sponsor regulatory lead within the same timeline used for reporting to regulatory authorities.

7.6. Pregnancy

Pregnancy is a contraindication to enrollment in the study. Pregnancy occurring during the study period, although not considered an SAE, must be reported to the NIH, local IRB and Sponsor within the same timelines as an SAE. The pregnancy will be recorded on the appropriate case report form. The drug will be discontinued immediately and subject discontinued from the trial, but the pregnancy will be followed until final outcome. Any associated AEs or SAEs that occur to the

mother or fetus/child will be recorded in the AE case report form or CIOMS form for SAEs.

8. STUDY MEASUREMENTS AND DATA COLLECTION

8.1. Assessment of exercise capacity

We will use a supine bicycle exercise protocol in conjunction with expired gas analysis to assess oxygen consumption (VO₂) during exercise. Subjects will perform a maximal exertion-limited exercise test using a graded-exercise protocol. We will use a supine cycle ergometer designed for stress echocardiography (Stress Echo Ergometer 1505, Medical Positioning, Inc, Kansas City, MO). Subjects will undergo expired gas analysis with a Parvo Medics True One 2400 device (Parvo Medics, Sandy, UT), an Innocor device (Innovision Inc) or equivalent. Resistance began at 15 W for 3 minutes, increasing to 25 W for 3 minutes, and then increasing by 25 W every 3 minutes thereafter. Breath-by-breath information will be recorded. We will use custom-designed software already developed in Matlab (MathWorks, Natick, MA) at our lab for offline processing and quantification of all exercise data.⁽⁸⁵⁾ All data quantification will be blinded to treatment. Total work performed will be computed and exercise efficiency will be defined as (total work/total oxygen consumed). Exercise efficiency is not a formal endpoint of the trial, but will be used to interpret changes in the co-primary outcomes. After these exercises, we will use a device that uses Near Infrared Spectroscopy [NIRS] to measure the oxygen levels in the left calf and forearm muscles (Portamon and Portalite devices, Artemis, Netherlands).

8.2. Quality of life

Quality of life will be assessed with the Kansas City Cardiomyopathy Questionnaire (KCCQ).⁽⁸⁶⁾ We will administer the KCCQ to subjects prior to randomization and at the end of each intervention phase (6-week time point in both phases). This is a validated 23-item questionnaire that assess physical function, symptoms, social function, self-efficacy and knowledge, and quality of life. It has been used extensively in heart failure studies (http://cvoutcomes.org/pages/3214)

8.3. Doppler Echocardiography

This procedure is similar to clinical cardiac echocardiograms. An ultrasound probe will be placed on the surface of the skin to obtain images of the heart. This takes approximately 20 minutes. This will occur at all three visits.

Measurement of LV filling and myocardial strain: given that inorganic nitrate may also induce venodilation and myocardial effects, we will also assess the effects of potassium nitrate on (1) Early mitral annular early diastolic tissue velocity; (2) The ratio of early diastolic mitral inflow velocity to mitral annular tissue velocity (a surrogate of LV filling pressures); (3) Peak early diastolic intraventricular pressure gradient, a marker of ventricular relaxation, assessed with color M-mode interrogations of mitral inflow.^(87,88) We note that the latter is not simply based on the inflow propagation velocity, but rather on solving Euler momentum equation.⁽⁸⁷⁾ This method is able to accurately assess LV relaxation⁽⁸⁷⁾. Systolic function will be assessed via systolic

myocardial strain (using speckle tracking echocardiography), which we have successfully applied in previous studies.^(66,69,89)

8.4. Measurement of late systolic load and arterial wave reflections:

We will use a high-fidelity Millar applanation tonometer⁽⁵⁴⁾ to record carotid pressure waveforms, which will be calibrated using brachial artery pressures. Central arterial tonometric recordings and Doppler flow velocity files will be processed off-line using custom-designed software written in Matlab (The Mathworks, Natick, MA) as previously described.^(66,90) We have successfully implemented this method in multiple previous studies^(8,57,66,67,91) and have published a tutorial detailing our analysis methods.^(8,53) After signal-averaging of pressure and flow, time alignment of carotid pressure and LV outflow curves will be performed to maximize concordance of the rapid systolic upstroke of pressure and flow, concordance of the dicrotic notch and cessation of flow, zero value of the phase angle of higher-frequency harmonics (7th to 10th) of input impedance, and linearity of the early systolic pressure-flow relationship.⁽⁹⁰⁾ After computation of aortic input impedance, proximal aortic characteristic impedance (Zc) will be computed in the frequency domain as previously described.⁽⁹⁰⁾ Pressure and flow harmonics were separated into forward and backward components using standard wave separation analysis.^(8,53,90,92) The sum of forward and backward pressure harmonics yields the forward and backward waves, respectively. We will assess the reflection coefficient in the first 3 harmonics. A reflection coefficient (Γ) is derived from the ratio of two sine waves, it is a complex number with an amplitude and phase-angle, which can correspond to different degrees of destructive or constructive interference between forward and backward waves. Therefore, the net-effect of reflections will be expressed as the real part of Γ , which becomes increasingly positive as pressure from wave reflections increases (constructive interference), and negative when destructive interference leads to a net decrease in pressure by wave reflections at a given harmonic.⁽⁹³⁾ Since all harmonics of wave reflection contribute variably to systolic LV load, our primary measure of late systolic load will be the net pressure related to wave reflections during ejection in the time domain, which better represents the impact of reflections on LV afterload. We will first compute the product of flow and aortic Zc (QZc product), which represents the pressure resulting from the interaction of blood flow with aortic root Zc.^(8,54) The relation between QZc and measured pressure reveals the direct effect of wave reflections on the arterial system.⁽⁹⁴⁾ We will therefore quantify the additional ejection-phase pressure load from wave reflections arising distal to the root (i.e., reflection-related pressure time integral during ejection, as the difference between measured pressure and the QZc product). Carotid-femoral pulse wave velocity (PWV), an index of large artery stiffness, (95,96) will also be measured (54,97) using a Sphygmocor device (Atcor Medical).⁽⁹⁵⁾ We will also measure carotid-radial PWV using the Sphygmocor device. PWV is not a formal endpoint of this trial, since our pilot trial did not demonstrate an effect of nitrate-rich beetroot juice on this endpoint (unpublished data). However, it may aid in interpreting changes in pulsatile hemodynamics in the trial. Similarly, when available, arterial tonometry may be performed during and immediately after exercise for exploratory purposes.
